### 5.6.2 Discontinuation of study treatment

Discontinuation of study drug for a patient occurs when study drug is stopped earlier than the protocol planned duration, and can be initiated by either the patient or the investigator.

Patients may voluntarily discontinue study drug (discontinue double-blind study drug but continue with study participation) at any time. **Patients who wish to discontinue double-blind study drug will be asked to remain in the study and complete all study visits. Patients withdrawn from study drug will receive SoC asthma therapy according to investigator judgment.**

The investigator must discontinue study drug for a given patient if, on balance, he/she believes that continuation of study drug would negatively impact the risk/benefit of trial participation.

Study drug **must** be discontinued under the following circumstances:

- Patient wish;
- Pregnancy (see [Section 6.5.6](#) and [Section 7.6](#));
- Any situation in which study participation might result in a safety risk to the patient;
- Female patients non-compliant with the chosen effective method of contraception during the study. The investigator must provide appropriate advice on the continued use of effective contraception for at least one week (at least 5 half-lives of QAW039) after study drug discontinuation and follow up with the subject as appropriate at least to the end of this period;
- Liver laboratory test abnormality / event (see [Appendix 2](#));
- Abnormal liver laboratory results requiring discontinuation – refer to [Table 14-2](#);

- If the investigator considers it appropriate after the confirmation of a liver safety monitoring signal:
  - ALT or AST  $\geq 5$ xULN, **or**
  - ALT or AST  $\geq 2.5$ xULN **and** total bilirubin  $\geq 1.5$ xULN ([Appendix 2](#));
- Any laboratory abnormalities that in the judgment of the investigator, taking into consideration the subject's overall status, prevents the subject from continuing participation in the study;
- Premature unblinding of study drug for a patient for any reason;
- Total white blood cell count  $<1000$  cells/ $\mu$ L;
- If patients on statin therapy complain of persistent muscle pain without any obvious cause for greater than 3 days accompanied by increase in CK levels  $>10$  x ULN or persistent intolerable muscle pain regardless of the accompanying CK level;

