## 14 Appendix 2: Liver event and laboratory trigger definitions and follow-up requirements

**Table 14-1 Liver Event and Laboratory Trigger Definitions**

	Definition/ threshold
LIVER LABORATORY TRIGGERS	3 x ULN < ALT / AST ≤ 5 x ULN 1.5 x ULN < TBL ≤ 2 x ULN
LIVER EVENTS	ALT or AST > 5 x ULN ALP > 2 x ULN (in the absence of known bone pathology) TBL > 2 x ULN (in the absence of known Gilbert syndrome) ALT or AST > 3 x ULN and INR > 1.5 Potential Hy's Law cases (defined as ALT or AST > 3 x ULN and TBL > 2 x ULN [mainly conjugated fraction] without notable increase in ALP to > 2 x ULN) Any clinical event of jaundice (or equivalent term) ALT or AST > 3 x ULN accompanied by (general) malaise, fatigue, abdominal pain, nausea, or vomiting, or rash with eosinophilia Any adverse event potentially indicative of a liver toxicity*

\*These events cover the following: hepatic failure, fibrosis and cirrhosis, and other liver damage-related conditions; the non-infectious hepatitis; the benign, malignant and unspecified liver neoplasms.

Abbreviations: ULN (upper limit of normal), ALT (alanine aminotransferase), AST (aspartate aminotransferase), TBL (total bilirubin), ALP (alkaline phosphatase), INR (international normalized ratio).

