**Table 14-2 Follow Up Requirements for Liver Events and Laboratory Triggers**

Criteria	Actions required	Follow-up monitoring
Potential Hy's Law case a	Discontinue the study treatment immediately Hospitalize, if clinically appropriate Establish causality Complete liver CRF	ALT, AST, TBL, Alb, PT/INR, ALP and γGT until resolution c (frequency at investigator discretion)
ALT or AST		
> 8 x ULN	Discontinue the study treatment immediately Hospitalize if clinically appropriate Establish causality Complete liver CRF	ALT, AST, TBL, Alb, PT/INR, ALP and γGT until resolution c (frequency at investigator discretion)
> 3 x ULN and INR > 1.5	Discontinue the study treatment immediately Hospitalize, if clinically appropriate Establish causality Complete liver CRF	ALT, AST, TBL, Alb, PT/INR, ALP and γGT until resolution c (frequency at investigator discretion)
> 5 to ≤ 8 x ULN	Repeat LFT within 48 hours If elevation persists, continue follow-up monitoring If elevation persists for more than 2 weeks, discontinue the study drug Establish causality Complete liver CRF	ALT, AST, TBL, Alb, PT/INR, ALP and γGT until resolution c (frequency at investigator discretion)
> 3 x ULN accompanied by symptoms b	Discontinue the study treatment immediately Hospitalize if clinically appropriate	ALT, AST, TBL, Alb, PT/INR, ALP and γGT until resolution c (frequency at investigator discretion)

Criteria	Actions required	Follow-up monitoring
	Establish causality Complete liver CRF	
> 3 to ≤ 5 × ULN (patient is asymptomatic)	Repeat LFT within the next week If elevation is confirmed, initiate close observation of the patient	ALT, AST, TBL, Alb, PT/INR, ALP and γGT until resolution c (frequency at investigator discretion)
ALP (isolated)		
> 2 × ULN (in the absence of known bone pathology)	Repeat LFT within 48 hours If elevation persists, establish causality Complete liver CRF	Investigator discretion Monitor LFT within 1 to 4 weeks or at next visit
TBL (isolated)		
> 2 × ULN (in the absence of known Gilbert syndrome)	Repeat LFT within 48 hours If elevation persists, discontinue the study drug immediately Hospitalize if clinically appropriate Establish causality Complete liver CRF	ALT, AST, TBL, Alb, PT/INR, ALP and γGT until resolution c (frequency at investigator discretion) Test for hemolysis (e.g., reticulocytes, haptoglobin, unconjugated [indirect] bilirubin)

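### Protocol 5.6.2, 7.3 and Appendix 2 give different liver thresholds and different degrees of obligation for stopping study drug

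*Protocol*

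**What the plan says.** Four places in the protocol govern stopping study drug for liver findings.

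**Section 5.6.2.** The list is introduced by "Study drug must be discontinued under the following circumstances". Three of its items concern the liver:

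- (i) "Liver laboratory test abnormality / event", with a pointer to Appendix 2 and no threshold.
- (ii) "Abnormal liver laboratory results requiring discontinuation", with a reference to Table 14-2.
- (iii) "If the investigator considers it appropriate after the confirmation of a liver safety monitoring signal", followed by two limbs: ALT or AST at least 5 x ULN, or ALT or AST at least 2.5 x ULN together with total bilirubin at least 1.5 x ULN. Appendix 2 is cited as the source.

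**Section 7.3.** A confirmed laboratory trigger leads to close observation, and interruption is to be considered. For liver events, discontinuation is to be done where appropriate. Detail is deferred to Table 14-2.

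**Table 14-1 (Appendix 2).** ALT/AST triggers run from above 3 to 5 x ULN, and ALT/AST events start above 5 x ULN. The combined ALT/AST and bilirubin criterion is "ALT or AST > 3 x ULN and TBL > 2 x ULN", without a notable rise in ALP.

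**Table 14-2 (Appendix 2).** The required action depends on the row:

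- Immediate stop: potential Hy's Law, ALT/AST above 8 x ULN, ALT/AST above 3 x ULN with INR above 1.5 or with symptoms, and jaundice.
- ALT/AST above 5 to 8 x ULN: "If elevation persists for more than 2 weeks, discontinue the study drug".
- Isolated bilirubin above 2 x ULN: stop if it persists on repeat.
- Asymptomatic ALT/AST above 3 to 5 x ULN: repeat, then "If elevation is confirmed, initiate close observation of the patient". The row for bilirubin above 1.5 to 2 x ULN is worded in the same way.
- Isolated ALP above 2 x ULN: repeat and, if it persists, establish the cause.

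**The concern.** These texts differ in two ways. The thresholds differ: 5.6.2 attributes to Appendix 2 a combination that is not there, and it uses a different inequality at 5 x ULN. The force of the instruction also differs: the same laboratory result can fall under a mandatory stop, a stop at the investigator's discretion, or a row that states no stop.

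What is at stake is consistent handling of a safety rule. Section 3.6 describes a major acyl glucuronide metabolite that partially binds plasma proteins, and an uncertain link between such binding and idiosyncratic reactions. Appendix 4 counts every liver trigger or event as a potential idiosyncratic reaction, and under 7.7 the DMC reviews these events regularly. Section 7.3 sets out to provide a standardized process. With the present wording, two sites could treat the same result differently, and a monitor could not say consistently which of them had deviated.

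**Working it through.** No sample size, power or alpha figure is involved, so the check sets the rules side by side. Test results are in multiples of ULN. Values not listed are taken as normal, and the patient as asymptomatic. Item (i) is read literally, as a stop for anything that Table 14-1 calls a trigger or event.

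| Result | 5.6.2 (i), literal | 5.6.2 (iii) | Table 14-2 |
|---|---|---|---|
| ALT 4 | stop | not reached | repeat, observe; no stop stated |
| ALP 2.5, isolated | stop | not reached | repeat, establish cause; no stop stated |
| Bilirubin 1.6, isolated | stop | not reached | repeat, observe; no stop stated |
| ALT 2.7, bilirubin 1.6 | stop | discretion | only the bilirubin row: repeat, observe |
| ALT 2.7, bilirubin 1.5 | no trigger met | discretion | no row |
| ALT 5.0 | stop | discretion | row above 3 to 5: repeat, observe |
| ALT 6 | stop | discretion | stop if it persists beyond 2 weeks |
| ALT 9 | stop | discretion | immediate stop |
| ALT 4, bilirubin 2.5 | stop | discretion | immediate stop (potential Hy's Law) |

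The comparison shows four things.

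1. **Item (i) is wider than Table 14-2.** In the first three rows its literal wording says stop, and the table states no stop. ALP above 2 x ULN is a defined liver event, not only a trigger. For an adverse event potentially indicative of liver toxicity, the table asks only that interruption or discontinuation be considered.

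2. **Item (iii) cites a criterion that Appendix 2 does not contain.** Nothing in Tables 14-1 or 14-2 uses 2.5 x ULN, or pairs ALT/AST with bilirubin at 1.5 x ULN. The fifth row meets item (iii) and no row of Table 14-2. In the fourth row, the only table entry reached is one headed as isolated bilirubin.

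3. **The boundary differs.** At exactly 5 x ULN, item (iii) applies because it uses at least 5. Appendix 2 starts above 5, so the same result falls in the observe row.

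4. **Item (iii) overlaps firmer rules.** Its first limb has no upper bound. It therefore covers above 5 to 8 x ULN, where the table has the two-week rule, and above 8 x ULN, where the table requires an immediate stop with no confirmation step. Its second limb covers potential Hy's Law cases in the same way. Section 7.3 adds a third formulation for these events: stop where appropriate.

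ALT/AST of 2.5 to 3 x ULN with normal bilirubin is not in dispute between item (iii) and Appendix 2. It meets neither limb of the item and no Appendix 2 trigger.

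**The case against.** A reader might infer that sites cannot follow 5.6.2 and Appendix 2 together. The documents do not support that. Item (ii) brings the Table 14-2 stops into 5.6.2, and 7.3 also sends sites to that table for detail. Item (iii) only adds an optional stop and cancels nothing in the table. Item (i) carries its own pointer to Appendix 2 and can be read as deferring to it. Even on the literal reading, the observe-only rows do not forbid stopping, so a site that stops, repeats the test and observes has satisfied both texts. Discretion inside the mandatory list is not unique to this item either: the same list includes laboratory abnormalities left to the investigator's judgment.

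A reader might also infer that every liver-related stop changes the primary analysis through jump-to-reference imputation. Under Protocol 9.4.3 and SAP 2.5.4, that imputation applies to missing data after discontinuation in the QAW039 arm. Data retrieved after stopping stay in the analysis, and 5.6.2 asks patients who stop to complete all visits.

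The practical reach is limited as well. Table 6-1 schedules central chemistry only at Visits 1, 201, TD and 299. The last dose is given at Week 12, which is Visit 299, so a result from that visit cannot shorten the treatment period. Entry criteria exclude ALT/AST above 2.0 x ULN or bilirubin above 1.3 x ULN at Visit 1. During treatment the rules would therefore act mainly on unscheduled tests, and on a Visit 201 result if it is reported after dosing has begun.

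All of this stands, and it limits the point. It does not remove it. If item (i) only defers to Appendix 2, it largely duplicates item (ii); if it means more, it departs from the table. The missing 2.5/1.5 criterion and the mismatch at 5 x ULN are errors on any reading.

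**Conclusion.** The point holds as an inconsistency in thresholds and in degrees of obligation across 5.6.2, 7.3 and Appendix 2. Two parts need no interpretation: the cross-reference to a combination that Appendix 2 does not contain, and at least 5 against above 5. The overlap of discretionary with mandatory stops is also plain on the page, although both can be obeyed. The gap between item (i) and the observe-only rows depends on reading item (i) literally.

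The size cannot be given. The documents assume 15% treatment discontinuation overall and do not say how much of it would be liver-related. No effect on power, alpha or the primary analysis is shown. Because this is a patient-safety stopping rule, it is more than a clerical matter and should be corrected. Which threshold or action is clinically right is not judged here.

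**What to change.** Reconcile 5.6.2, 7.3 and Tables 14-1 and 14-2 into one set of liver thresholds. Mark each as a mandatory stop or as at investigator discretion, and use the same inequality at each boundary. Either merge item (i) with item (ii) or state what it adds. Keep cross-references only to criteria that exist in Appendix 2. The clinical team decides which rule applies in each row.

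The cost is protocol wording in the next amendment, with notice to sites and monitors. The efficacy analysis and the sample size need no change.

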#### 5.6.2.1 Asthma worsening alerts

The data captured in the patient eDiary will be used in conjunction with the patient's asthma characteristics to monitor the patient's asthma. Patients will be instructed to call the study site if they experience symptoms of worsening asthma. Additionally, the eDiary will be

programed to generate some alerts of signs of possible worsening asthma based on data collected. These alerts will be sent to the patient and/or to the investigator.

The patient's personal best PEF in the clinic at Visit 101 will be set as the patient's baseline for the placebo run-in period, and the personal best PEF in the clinic at Visit 199 will be set as the patient's baseline for the treatment period.

### **5.6.3 Withdrawal of informed consent**

Patients may voluntarily withdraw consent to participate in the study for any reason at any time. Withdrawal of consent from the study is defined as when a patient:

- Does not want to participate in the study anymore

and

- Does not want any further visits or assessments

and

- Does not want any further study related contacts

and

- Does not allow analysis of already obtained biologic material

In this situation, the investigator must make every effort (e.g. telephone, e-mail, letter) to determine the primary reason for the patient's decision to withdraw his/her consent and record this information.

Study treatment must be discontinued and no further assessments conducted, and the data that would have been collected at subsequent visits will be considered missing.

Further attempts to contact the patient are not allowed unless safety findings require communicating or follow-up.

All efforts should be made to complete the assessments prior to study withdrawal. A final evaluation at the time of the patient's study withdrawal should be made as detailed in the assessment table below.

### **5.6.4 Loss to follow-up**

For patients whose status is unclear because they fail to appear for study visits without stating an intention to discontinue or withdraw, the investigator must show "due diligence" by documenting in the source documents steps taken to contact the subject, e.g. dates of telephone calls, registered letters, etc. A patient cannot be considered as lost to follow-up until the time point of his/her scheduled end of study visit has passed.

### **5.6.5 Early study termination by the sponsor**

The study can be terminated by Novartis at any time for any reason. This may include reasons related to the benefit risk assessment of participating in the study, practical reasons, or for regulatory or medical reasons (including slow enrolment). Should this be necessary, the patient must be seen as soon as possible and treated as a prematurely discontinued patient. The investigator may be informed of additional procedures to be followed in order to ensure

that adequate consideration is given to the protection of the patient's interests. The investigator will be responsible for informing the Institutional Review Board/Independent Ethics Committee (IRBs/IECs) of the early termination of the trial.

## 6 Visit schedule and assessments

Visits must be scheduled to allow randomized study drug to be taken in the morning.

Table 6-1 lists all of the assessments and indicates with an "X" or "S" when the visits are performed. Assessments marked with "S" are documented in source documentation only and will not be entered into the eCRF.

Patients must be seen for all visits on the designated day, or as close to it as possible. Missed or rescheduled visits should not lead to automatic discontinuation. Patients who discontinue study drug before completing the study and accept to remain in the study will return for study visits as described in Section 5.6.2. If they fail to return for these assessments for unknown reasons, every effort should be made to contact them as specified in Section 5.6.2. At the very least, patients should be asked if they can be contacted by phone by study personnel at the date they would have been scheduled to end the follow up period (4 weeks after premature study drug discontinuation) to ask about concomitant medication use, surgery and procedures, SAEs, AEs and asthma exacerbations.

**Patients will be required to attend the clinic in the morning at approximately the same time, so that pre-dose FEV1 assessments can be performed between 6 AM and 10 AM ±1 hour.** Efficacy and safety assessments will be completed prior to QAW039 or placebo administration in the clinic.

When the following assessments are scheduled to be performed at the same time-point, the order of priority will be as follows:

1. **Question on medication withholding for spirometry**

If the patient has not withheld medications as specified in the protocol before a particular visit, the visit must be rescheduled;

2. **Patient Reported Outcome (PRO) instruments** to be completed in the following order:

ACQ-5, AQLQ+12, [REDACTED] at certain clinic visits;

3. **Vital signs;**

4. **ECGs;**

5. **Samples for urinalysis/hematology/blood chemistry** (At Visit 1, there is no specified order for collection of samples. At all other applicable visits, collect samples prior to the 1st pre-dose spirometry [which is the -45 minute pre-dose spirometry] or between the 1st and 2nd pre-dose spirometry measurements);

6. [REDACTED]

7. **Spirometry.** Spirometry assessments must be timed so that the Visit 1 spirometry assessment and all pre-dose spirometry assessments can be performed between 6 AM and

10 AM  $\pm$ 1 hour and other tests must be performed as close as possible to those spirometry times. During the treatment period, two pre-dose spirometry assessments must be performed as follows:

- First pre-dose spirometry assessment: **approximately** 45 minutes prior to the dosing of study drug at the clinic visit.
  - Second pre-dose spirometry assessment: **approximately** 15 minutes prior to the dosing of study drug at the clinic visit.
8. **Reversibility at certain visits (spirometry after administration of SABA) may be performed after 10 AM  $\pm$ 1 hour.**
  9. **In-clinic witnessed dosing of study drug.**

**Table 6-1 Assessment schedule**

Period	Screen	Placebo Run-in		Treatment						Follow-up	Notes
		101	199	201	202	203	204	TD	299		
Visit Number (Site visits)	1	101	199	201	202	203	204	TD	299	301	Follow-up Visit 301 is only applicable for patients not participating in the safety study.
Treatment Week	-3	-1	0	0	2	4	8	TD	12	16	Visit 199 and Visit 201 occur on the same day.
Treatment Day	-21	-7	1	1	14	28	56		84	112	
Informed consent and assent (if applicable)	X										ICF must be obtained within 14 days of Visit 1 or at Visit 1.
Ask question on withholding of medication before clinic visits	S		S		S	S	S	S	S		If the patient has not withheld medications as specified in the protocol before a particular visit, the visit must be rescheduled.
Demographics	X										
Medical history	X										
Medical History – Protocol solicited events for asthma	X										
Asthma exacerbation history	X										
Smoking history	X										
Prior/concomitant medication (asthma and non-asthma medications) review	X		X		X	X	X	X	X		
Inclusion/exclusion criteria	X		X								
Review and record surgeries and procedures	X		X		X	X	X	X	X		
Physical examination	S							S	S		
Abbreviated physical examination			S		S	S	S				Heart and lungs only.
ACQ-5 in clinic			X								
AQLQ+12 in clinic			X			X		X	X		

[figure not shown]
Period	Screen	Placebo Run-in		Treatment						Follow-up	Notes
Visit Number (Site visits)	1	101	199	201	202	203	204	TD	299	301	Follow-up Visit 301 is only applicable for patients not participating in the safety study.
Treatment Week	-3	-1	0	0	2	4	8	TD	12	16	Visit 199 and Visit 201 occur on the same day.
Treatment Day	-21	-7	1	1	14	28	56		84	112	
Train patient and assess patient's ability to use eDiary/ePEF and dispense eDiary/ePEF	S										
Review eDiary /ePEF compliance		S	S †								† eDiary/ePEF compliance must be assessed prior to randomizing the patient.
Review eDiary/ePEF entries		S	S		S	S	S	S	S		
Height	X							X	X		
Weight	X		X					X	X		
Vital signs	X	X	X		X	X	X	X	X		Systolic/diastolic blood pressure, radial pulse (sitting), and body temperature.
Electrocardiogram	X							X			
Electrocardiogram (Pre-dose)				X					X		
Pregnancy test—serum (women of child bearing potential)	X										Pregnancy testing will begin at the visit a patient is first identified as being of child bearing potential. If positive, the patient must not be randomized.
Pregnancy test—urine dipstick test in clinic (women of child bearing potential)			X			X	X	X	X	X	Pregnancy testing will begin at the visit a patient is first identified as being of child bearing potential. A positive urine pregnancy test requires immediate interruption of study drug until serum β-hCG is performed and found to be

Period	Screen	Placebo Run-in		Treatment						Follow-up	Notes
Visit Number (Site visits)	1	101	199	201	202	203	204	TD	299	301	Follow-up Visit 301 is only applicable for patients not participating in the safety study.
Treatment Week	-3	-1	0	0	2	4	8	TD	12	16	Visit 199 and Visit 201 occur on the same day.
Treatment Day	-21	-7	1	1	14	28	56		84	112	
											negative. If positive, the patient must be discontinued from study drug.
Urinalysis and urine chemistry (central laboratory)	X			X				X	X		
Blood sample for hematology and chemistry (central laboratory)	X			X				X	X		No fasting requirement prior to blood sampling.
Blood sample for RAST/ImmunoCAP test (central laboratory)	X										
Review Visit 1 laboratory results		S									If results for chemistry, hematology, HbA1c, RAST/ImmunoCAP, urine chemistry and urinalysis are missing, obtain a repeat for the missing result.
Parasitic screening	S										Only if required by health authority and/or ethics committee/ institutional review board. Sites should use local laboratories.
Spirometry (centralized)	X							X			
1 st Pre-dose Spirometry (centralized) approximately - 45 min. pre-dose		X		X	X	X	X		X		To be performed approximately 45 min. prior to in-clinic witnessed study drug administration.
2 nd pre-dose Spirometry (centralized) approximately -15 min. pre-dose		X ε		X	X	X	X		X		To be performed approximately 15 min. prior to in-clinic witnessed study drug administration.

Period	Screen	Placebo Run-in		Treatment						Follow-up	Notes
Visit Number (Site visits)	1	101	199	201	202	203	204	TD	299	301	Follow-up Visit 301 is only applicable for patients not participating in the safety study.
Treatment Week	-3	-1	0	0	2	4	8	TD	12	16	Visit 199 and Visit 201 occur on the same day.
Treatment Day	-21	-7	1	1	14	28	56		84	112	
											£To be performed prior to reversibility test.
Reversibility test (spirometry after administration of short-acting $\beta$ -agonist [SABA])	X**	X <math>\alpha</math>,<math>\beta</math>**									
¤To be performed prior to in-clinic witnessed study drug administration.
 
£To be performed after the second (-15 min.) pre-dose spirometry (may be performed after 10 AM <math>\pm</math> 1 h).
 
**If reversibility is NOT demonstrated at Visit 1, reversibility will be attempted at Visit 101. If not achieved, then one additional attempt allowed within 4 days following Visit 101.

Review Visit 1 or Visit 101 or the one additional attempt reversibility result from overread			S								
Asthma exacerbation monitoring	X	X	X	X	X	X	X	X	X	X	In case of an asthma exacerbation, the patient should be encouraged by the site to contact it for advice. If necessary, an unscheduled visit to the site may be arranged.
Serious adverse event monitoring	X	X	X	X	X	X	X	X	X	X	
Adverse event monitoring	X	X	X	X	X	X	X	X	X		
Liver event monitoring	X	X	X	X	X	X	X	X	X	X	If applicable, review lab results and clinical events as per Section 7.3 .
Renal event monitoring	X			X				X	X		If applicable, review lab results as per Section 7.4 .

Period	Screen	Placebo Run-in		Treatment						Follow-up	Notes
Visit Number (Site visits)	1	101	199	201	202	203	204	TD	299	301	Follow-up Visit 301 is only applicable for patients not participating in the safety study.
Treatment Week	-3	-1	0	0	2	4	8	TD	12	16	Visit 199 and Visit 201 occur on the same day.
Treatment Day	-21	-7	1	1	14	28	56		84	112	
Record deaths	X	X	X	X	X	X	X	X	X	X	
Contact IRT	S	S	S	S	S	S	S	S	S	S	
Randomize patient through IRT				S							
Assess and dispense rescue SABA to be used on an as-needed basis	S*	S	S	S	S	S	S	S	S**		*dispense SABA only **assess SABA only
Dispense study drug		S		S	S	S	S				Patients will be instructed to take study drug in the morning.
Assess compliance with study drug (count tablets in returned bottles)			S		S	S	S	S	S		
In-clinic witnessed study drug intake		X		X	X	X	X		X		Complete Dosage Administration Record (DAR)-Visit – at site visit.
Complete Study Drug Dosage Administration Record-Summary page			X		X	X	X	X	X		Complete DAR- Summary at each indicated visit to record compliance
Complete Study Disposition page (screening)	X										
Complete Study Disposition page (run-in)			X								
Complete Study Disposition page (end of treatment )									X		
Complete Study Disposition page (follow-up )										X	For patients not participating in the safety study.
Complete Withdrawal of	X	X	X	X	X	X	X	X	X	X	

Period	Screen	Placebo Run-in		Treatment						Follow-up	Notes
Visit Number (Site visits)	1	101	199	201	202	203	204	TD	299	301	Follow-up Visit 301 is only applicable for patients not participating in the safety study.
Treatment Week	-3	-1	0	0	2	4	8	TD	12	16	Visit 199 and Visit 201 occur on the same day.
Treatment Day	-21	-7	1	1	14	28	56		84	112	
informed consent form (if patient withdraws consent)											
Re-screening of patient	X										Re-screening of patients is permitted once. Once a patient enters the placebo run-in period, the patient may not be re-screened. If a patient is re-screened, a new informed consent (and assent if applicable) must be obtained.
Appointment for next clinic visit	S	S		S	S	S	S	S	S		
Dispense patient card	S										
Discuss optional participation in safety study									S		
Collect patient card									S*	S	* If participating in the safety study.

Abbreviations: TD (treatment discontinuation), ICF (informed consent form), ACQ-5 (asthma control questionnaire-5), AQLQ+12 (asthma quality of life questionnaire for 12 years and older, [REDACTED]), eDiary/ePEF (electronic peak expiratory flow), ECG (electrocardiogram), RAST (radioallergosorbent test), HbA1c (hemoglobin A1c), [REDACTED], IRT (interactive response technology).

